7.5 Description of Subgroups to be Analyzed

Details will be provided in the Statistical Analysis Plan (SAP) for any proposed subgroup analyses (e.g. patients with all baseline IELTs were ≤ 60 seconds).

7.6 Statistical Analysis Methodology

Summary statistics will be provided for all study endpoints. For continuous endpoints n (number of patients included in the analysis), mean, SD, median, minimum, maximum, Quartile 1, and Quartile 3 will be provided. For categorical endpoints, the number and frequency in each category will be provided. Adjusted effect size and 95% CI will be displayed for all treatment comparisons.

For the purpose of e-diary data analyses, the treatment assessment period will include all assessments done between end of treatment and end of treatment minus 28 days, if patients have a sufficient amount of assessments within this time window. The time window may be extended back for patients without a sufficient amount of assessments within the predefined time window. Additional details will be provided in the SAP regarding the derivation of the treatment assessment period.

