13.2	Appendix 2: Evaluation Instruments	80
13.2.1	Clinical Global Impression of Change (CGIC)	80
13.2.2	Premature Ejaculation Profile (PEP)	80

13.2.3 International Index of Erectile Function (IIEF) 81

13.2.4 Patient Health Questionnaire 9 (PHQ-9) 88

13.2.5 Columbia-Suicide Severity Rating Scale (C-SSRS)..... 89

13.3 Appendix 3: Laboratory Safety Tests..... 93

13.4 Appendix 4: Amendment 1.0.....95

List of Tables

Table 13-1 Schedule of Events..... 78

List of Figures

Figure 3-1 Study Design..... 32

Figure 7-1 Overview of the Multiplicity Control 62

Protocol Synopsis

- Protocol Number:** IX-0105
- Title:** A Phase 2b, 8-Week, Double-Blind, Placebo-Controlled, Parallel-Group Study to Evaluate the Effects of 3 Different Dose Levels of IX-01 on Intravaginal Ejaculatory Latency Time (IELT), Patient-Reported Outcomes, and Safety in Men with Lifelong Premature Ejaculation (PE)
- Sponsor:** Ixcelsius Ltd.
[name]
[name], United Kingdom
- Study Phase:** Phase 2b
- Study Sites:** Approximately 30 sites in the United States
- Indication:** Premature Ejaculation
- Rationale:** In a previous clinical study, the selective oxytocin-receptor antagonist, IX-01 has been shown to prolong intravaginal ejaculatory latency time (IELT) and improve patient-reported outcomes in men with lifelong premature ejaculation (PE). This study is designed to explore the relationship between efficacy and dose.
- Objectives:**
- To determine the efficacy of 3 different dose levels of IX-01 to prolong IELT in men with PE.
 - To determine the efficacy of 3 different dose levels of IX-01 on Clinical Global Impression of Change (CGIC), control of ejaculation, ejaculation-related distress and interpersonal difficulty, and satisfaction with sexual intercourse in men with PE.
 - To determine the toleration and safety of 3 different dose levels of IX-01 taken as required in men with PE.
- Patient Population:**
- Men aged ≥ 18 years and ≤ 60 years in stable (≥ 6 months) heterosexual relationship and who have lifelong PE.
 - PE confirmed by IELT ≤ 1 minute on at least 75% of attempts at sexual intercourse during the run-in period.
 - Men meeting other aspects of International Society for Sexual Medicine (ISSM) definition including inability to delay ejaculation on all or nearly all vaginal penetrations and negative personal consequences such as distress, bother and frustration.

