Eligible patients will undergo one 8-week treatment period, during which time they are randomized to take IX-01, 400, 800, or 1200 mg or matching placebo. In order to maintain the double-blind, each dose will be presented as 3 caplets in blisters in single-dose units. Thus, for example, a patient randomized to 400 mg IX-01 will receive blister cards with each dose comprising one IX-01 400 mg caplet and two matching placebo caplets. Patients will complete an e-diary (LogPad) on all days during the treatment period that sexual activity is performed with or without the use of the study drug.

During the treatment period, patients will be expected to return to the study site and use their LogPad to complete the following questionnaires according to the study schedule:

- Premature Ejaculation Profile (PEP)
- International Index of Erectile Function (IIEF)
- Patient Health Questionnaire (PHQ-9)
- Patient Global Impression of Severity (PGIS)
- Clinical Global Impression of Change (CGIC) – Early Termination/Visit 5 only

The LogPad will provide results to the Investigator regarding whether or not the patient is required to complete the C-SSRS. The C-SSRS is mandatory at baseline, and is only mandatory at all other visits if the PHQ-9 total score is >9 , and/or the PHQ-9 Question 9 score is >0 ; it may also be administered at any time if clinically indicated, in the opinion of the Investigator. A final follow-up visit is conducted 2 weeks after the end of double-blind treatment. For more details of the procedures at each study visit, please refer to Section 6.

4 Patient Selection and Withdrawal Criteria

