7.6.1 Analysis of Primary Efficacy Endpoint

[figure not shown]
The primary efficacy analysis of the primary endpoint will be performed on the mITT population. Change from baseline in GM IELT over the treatment assessment period will be analyzed using a mixed linear model, including treatment and baseline IELT as fixed factors and type of site as a random factor.

The primary comparison of interest is IX-01 1200 mg versus placebo. If it is statistically significant at $\alpha=0.05$, then the following comparisons will be tested in the following order:

- IX-01 800 mg vs placebo group
- IX-01 400 mg vs placebo group

An overview of the approach to control for multiple comparisons is provided in Figure 7-1.

Figure 7-1 Overview of the Multiplicity Control

If at any point in the sequence statistical significance is not met, then subsequent analyses in the sequence cannot be deemed statistically significant. In such cases, nominal P values and 95% CI will be reported and interpreted in an exploratory manner. Irrespective of whether there are any statistically significant differences between treatment groups, IELT data from all treatment groups will also be used to model a possible dose response relationship. Further details on dose response analysis will be provided in the SAP.

The analyses above will be repeated using the Per-Protocol and ITT populations to examine the robustness of the primary results.

As a sensitivity analysis of the primary endpoint, a nonparametric approach will be carried out on the mITT population in order to obtain the median treatment effect and 95% CI.

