7.6.3 Safety Analyses

Safety analyses will be based on all patients included in the safety population.

Changes from baseline will be the absolute changes from baseline:

Change from baseline = raw value – baseline value

Study Drug Administration and Exposure: Study drug administration and exposure will be summarized and listed. Further details on study drug administration and exposure calculation will be given in the SAP.

Medical History: Medical history details recorded at screening will be summarized and listed according to the coded Medical Dictionary for Regulatory Activities (MedDRA) (latest version) by system organ class, preferred term, and treatment group.

Concomitant Medications: Previous and concomitant medications will be summarized according to the WHO Drug Dictionary (WHO-DD). The number and percentage of patients for each treatment group will be presented for previous and concomitant medications.

The patient will record in the LogPad whether he had any alcoholic drinks within 4 hours prior to sexual intercourse.

Adverse Events: Adverse events will be coded according to the coded MedDRA (latest version). Treatment-emergent AEs will be tabulated by system organ class, preferred term, and treatment group. Further details will be given in the SAP on the definition of TEAEs.

The following summary tables will be produced:

- TEAEs
- Serious TEAEs
- TEAEs leading to study drug discontinuation
- Treatment-related TEAEs leading to study drug discontinuation
- Treatment-related TEAEs
- Treatment-related serious TEAEs

All AEs recorded during the study (including non-treatment-emergent AEs) will be listed.

Physical Examination and Vital Signs: Abnormal physical examinations will be listed. Descriptive by-visit summaries of vital signs data will be presented by treatment group (including raw values and change from baseline). Vital signs will include blood pressure, heart rate, and temperature.

Height, Weight, and BMI: Baseline height, weight, and BMI will be summarized and listed. Weight and BMI as well as mean change from baseline will be summarized for Week 8 and end-of-study visits.

ECGs: Descriptive summaries of change in overall assessment of ECG data from baseline to Week 8 and end of study will be presented in a shift table (normal, abnormal [not clinically significant], and abnormal [clinically significant]) by treatment group.

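### Does counting intercourse attempts made without a dose undermine the primary IELT comparison or the dose-response model?

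*Combined protocol and SAP*

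**What the plan says.** Section 7.6 defines the window behind the primary endpoint: "the treatment assessment period will include all assessments done between end of treatment and end of treatment minus 28 days", provided there are enough assessments, with extension backwards otherwise. It sets no dosing condition. Section 3.1 has the diary completed "on all days during the treatment period that sexual activity is performed with or without the use of the study drug". Section 5.5 does not require daily dosing. Section 6.2 has the LogPad capture the date and time of both doses and attempts.

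The Synopsis gives the purpose: "This study is designed to explore the relationship between efficacy and dose". Section 7.6.1 adds that "IELT data from all treatment groups will also be used to model a possible dose response relationship", whether or not any comparison is significant. Its supportive work is a repeat in other analysis sets, "The analyses above will be repeated using the Per-Protocol and ITT populations to examine the robustness of the primary results", and a nonparametric analysis in the mITT Set.

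Several details are deferred. Section 7.6 says "Additional details will be provided in the SAP regarding the derivation of the treatment assessment period", Section 7.6.1 says "Further details on dose response analysis will be provided in the SAP", and Section 7.6.2.4 leaves missing-data sensitivity analyses of the primary endpoint to the SAP. The mITT definition in Section 7.4 counts only *analyzable* IELTs without defining the word. Section 7.6.3 states that "Study drug administration and exposure will be summarized and listed". The combined document contains no separate SAP text.

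**The concern.** The drug is taken as needed, so an attempt without a dose shows little of what that dose does. If such attempts are averaged in at a similar rate in every arm, the arms move closer together and the dose-response curve flattens. A weak slope could then reflect either the drug or missed doses. The stated repeats change the patients (Per-Protocol, ITT) or the method (nonparametric), never the attempts, so none of them separates the two explanations.

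Few attempts are needed for this to matter to one patient. The requested minimum is 8 attempts in 8 weeks, so a 28-day window holds about 8 × 28/56 = 4, and one undosed attempt is 25% of that patient's data.

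**Working it through.** **The plan's own figure.** Inputs from Section 7.3: difference 45 s, SD 70 s, two-sided alpha 0.05, groups of 44, 44, 66 and 66.

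- 44 v 66: SE = 70 × √(1/44 + 1/66) = 13.62 s; 45/13.62 = 3.30; power 90.6% (noncentral t) or 91.0% (normal).
- 44 v 44: SE = 70 × √(2/44) = 14.92 s; 45/14.92 = 3.02; power 84.6% or 85.4%.

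The stated 90% and 85% hold.

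**Dilution with the same undosed share f in each arm.** The documents do not give f. As an illustration, take the IX-0103 folds (Section 1.3.5: 3.6 on drug, 1.8 on placebo) as on-drug folds from a common baseline. The undiluted difference is then 3.6 − 1.8 = 1.8 baselines. A geometric mean mixes attempts on the log scale, so the share of the difference in seconds that is kept is:

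| Undosed attempts sit at | Formula | f = 10% | f = 25% |
|---|---|---|---|
| baseline | (3.6^(1−f) − 1.8^(1−f))/1.8 | 0.817 | 0.589 |
| placebo level | 2^(1−f) − 1 | 0.866 | 0.682 |
| half the drug effect | 2^(1−f/2) − 1 | 0.932 | 0.834 |

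On the log scale the dose-response slope keeps 1 − f (or 1 − f/2 in the last case). It shrinks but does not become flat.

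**Dilution with unequal shares.** Dosing is by choice, so f may differ by arm. With undosed attempts at baseline:

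- 5% active, 25% placebo: (3.6^0.95 − 1.8^0.75)/1.8 = (3.377 − 1.554)/1.8 = 1.013.
- 0% active, 10% placebo: (3.6 − 1.8^0.90)/1.8 = (3.6 − 1.697)/1.8 = 1.057.
- 25% active, 5% placebo: (3.6^0.75 − 1.8^0.95)/1.8 = (2.614 − 1.748)/1.8 = 0.481.

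So the direction is not fixed.

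**Power.** If 45 s were a pure on-drug effect and the SD stayed at 70 s, linear dilution at 20% would give 45 × 0.8 = 36.0 s and 75.3% power for 44 v 66. Neither condition is given. In IX-0103 the observed difference was 61.0 − 16.4 = 44.6 s, and the documents do not say that undosed attempts were left out of it, so 45 s may already be diluted. The SD in seconds also moves with the dilution. A simulation (20,000 trials per case, 44 v 66, change in seconds adjusted for baseline) used assumptions from outside the documents: baseline log-SD 0.4 and log-fold SD 0.86. From an undiluted 91.3%, power ran from 85.6% to 93.1% at f = 10% and from 72.2% to 95.1% at f = 25%. Even the sign of the change depends on the assumptions.

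**How large f might be.** Section 6.1 tells patients to attempt intercourse about 1 to 6 hours after a dose, and supplies at least 7 + 7 + 14 = 28 doses for about 8 requested attempts. Both point to a small share, though neither measures it.

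**Whether an on-drug split would be clean.** The half-life is about 12 hours (Section 1.3.5). In IX-0103 the mean was 14.6 doses; over 56 days that is one per 56/14.6 = 3.84 days, or 92 h. That is the gap between doses. An attempt at a random point in an even gap comes 46 h after the last dose on average, about 46/12 = 3.8 half-lives. Because dosing is capped at once a day, a second attempt on the same day or the next morning has no new dose but falls within about 2 half-lives. A filter on the 1 to 6 hour window would call it off-drug while drug is still present.

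**The case for a change.** The strongest case for a change is that it costs a paragraph, a filter and a table. The data exist, the study is about dose, and nothing stated can tell a weak drug from missed doses. If the undosed share proved small, reporting it by arm would strengthen the result. All of this is fair, and it stands that the protocol text names no analysis of dosed attempts only.

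Three further steps are needed to make it a defect, and none holds. First, the split need not be post hoc: the SAP is where the protocol places the window and dose-response rules, and it can specify the split before unblinding. Second, undosed attempts do not always pull the arms together, as the unequal-share cases show. Third, an on-drug analysis is not the purer answer. It selects attempts after randomization by something the patient chooses, drops some attempts with drug still present, and may leave some men with fewer than two usable IELTs.

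Some of the ground may also be covered already. A definition of *analyzable* could require a dose, in which case the dilution figures do not apply. The Per-Protocol Set removes patients with major deviations that affect evaluability of the primary parameter, which could include men who mostly did not dose, although an undosed attempt is not named as a deviation.

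**Conclusion.** No change to the plan. Averaging all attempts answers a sound question: what happens to IELT in men given this drug to use as needed. Followed as written, it gives a valid randomized comparison, and the stated power is right on its own inputs. The omission is a detail that the protocol openly leaves to its SAP and that an analyst can fill from the LogPad before unblinding.

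The possible dilution runs from 7% to 41% of the difference in seconds for an undosed share of 10% to 25%. It assumes equal shares in all arms and IX-0103 folds that are purely on-drug; with unequal shares the change can go either way. The share itself is unknown, and the dosing instructions and supply suggest that it is small. An on-drug analysis would be an optional, supportive addition. This conclusion would need another look only if the SAP were silent on the point and the diary showed a large undosed share, or one that differed clearly between arms.

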7.6.1 Analysis of Primary Efficacy Endpoint

[figure not shown]
The primary efficacy analysis of the primary endpoint will be performed on the mITT population. Change from baseline in GM IELT over the treatment assessment period will be analyzed using a mixed linear model, including treatment and baseline IELT as fixed factors and type of site as a random factor.

The primary comparison of interest is IX-01 1200 mg versus placebo. If it is statistically significant at $\alpha=0.05$, then the following comparisons will be tested in the following order:

- IX-01 800 mg vs placebo group
- IX-01 400 mg vs placebo group

An overview of the approach to control for multiple comparisons is provided in Figure 7-1.

Figure 7-1 Overview of the Multiplicity Control

If at any point in the sequence statistical significance is not met, then subsequent analyses in the sequence cannot be deemed statistically significant. In such cases, nominal P values and 95% CI will be reported and interpreted in an exploratory manner. Irrespective of whether there are any statistically significant differences between treatment groups, IELT data from all treatment groups will also be used to model a possible dose response relationship. Further details on dose response analysis will be provided in the SAP.

The analyses above will be repeated using the Per-Protocol and ITT populations to examine the robustness of the primary results.

As a sensitivity analysis of the primary endpoint, a nonparametric approach will be carried out on the mITT population in order to obtain the median treatment effect and 95% CI.

7.6.2 Analysis of Secondary Efficacy Endpoint

All secondary analyses will be carried out testing each dose group versus the placebo group on for the ITT population.

The same approach to control for multiple comparisons as proposed for the primary endpoint will be used for each secondary endpoint analysis.

7.6.2.1 Change From Baseline Endpoints

Analyses of e-diary data expressed in change from baseline over the treatment assessment period will be carried out using a mixed linear model. All analyses should include treatment, baseline IELT, and the baseline score of the analyzed endpoint as fixed effects and the site as a random effect. In addition to the mixed linear model, a nonparametric approach may be carried out for specific secondary endpoints. Further details will be provided in the SAP.

Change in score from baseline in each of the PEP questions (ie, Endpoint 17 of Section 7.2.2) will be carried out using a mixed-effect model repeated measure model. All analyses should include treatment, baseline IELT, the baseline score of the analyzed endpoint, the visit, and the interaction between visit and treatment as fixed effects and the site as a random effect. Visit will be considered as the repeated measurement.

7.6.2.2 Proportion Endpoints

For each analysis on proportion endpoint, difference in the proportions between each test group and placebo group will be tested using a logistic model. All analyses should include treatment, baseline IELT, and the type of site as factors. *P* values and adjusted odds ratios will be presented.

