During the treatment period, patients were required to return to the study site at Weeks 2, 4, and 8 and use their electronic diary (LogPad) to complete the Premature Ejaculation Profile (PEP) and other patient-reported outcomes. A follow-up visit was to be performed 2 weeks after the end of treatment.

The mean age of men in this study was 43 years, and the baseline GM IELT was < 30 seconds in both treatment groups. Patients randomized to IX-01 took a mean of 14.6 (range 1-59) doses during the study. Patients randomized to placebo took a mean of 13.0 (range 1-51) doses. Fifty (89.3%) and 23 (76.7%) patients (IX-01 and placebo, respectively) took the permitted maximum dose of 4 capsules at least once during the study.

Mean IELT values increased 3.6-fold from baseline for IX-01, compared with 1.8-fold for placebo. Mean IELT values increased by over 1 minute (61.0 seconds) for IX-01 compared with 16.4 seconds for placebo. The results also showed clinically and statistically significant improvements in perceived control of ejaculation and ejaculation-related personal distress at end of treatment for IX-01 compared with placebo. Twenty-one (44%) patients randomized to IX-01 rated their PE as improved at the end of treatment compared with 3 (13%) of patients randomized to placebo. There were also clinically and statistically significant

improvements for some of the results of the 4-week recall PEP, with 17 (33%) patients randomized to IX-01 improving their control of ejaculation to “fair,” “good,” or “very good” compared with one (3%) patient randomized to placebo. There was also a clinically and statistically significant difference in favor of IX-01 for the proportion of patients whose level of ejaculation-related distress improved to “moderate,” “a bit,” or “not at all,” 24 (46%) for patients randomized to IX-01 versus 4 (16%) for patients randomized to for placebo.

There were no serious and no severe AEs reported during this study. The proportions of patients reporting AEs were similar for IX-01 and placebo, with no AE reported by more than 2 patients in any treatment group. Two patients were discontinued from IX-01 for possibly treatment-related AEs: one for AE of increased transaminases that normalized during treatment and one for AE of nausea. There were no safety signals arising from review of vital signs, laboratory function test results, 12-lead ECGs, and other safety assessments.

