7.2.2 Other Secondary Efficacy Endpoints

The following other secondary efficacy endpoints will be analyzed:

1. Fold change from baseline in (arithmetic) mean IELT over the treatment assessment period.
2. Change from baseline in (arithmetic) mean IELT over the treatment assessment period.
3. Proportion of patients with GM IELT of ≥ 1 minute over the treatment assessment period.
4. Proportion of patients with GM IELT of ≥ 2 minutes over the treatment assessment period.
5. Proportion of patients with GM IELT of ≥ 3 minutes over the treatment assessment period.
6. Proportion of patients with GM IELT of ≥ 4 minutes over the treatment assessment period.
7. Proportion of patients with GM IELT of ≥ 5 minutes over the treatment assessment period.
8. Proportion of patients with GM IELT increase over the treatment assessment period of ≥ 45 seconds compared with baseline.
9. Proportion of patients with GM IELT increase over the treatment assessment period of ≥ 1 minute compared with baseline.
10. Percentage of intercourse attempts lasting > 1 minute over the treatment assessment period.
11. Percentage of intercourse attempts lasting > 2 minutes over the treatment assessment period.
12. Percentage of intercourse attempts lasting > 3 minutes over the treatment assessment period.
13. Percentage of intercourse attempts lasting > 4 minutes over the treatment assessment period.
14. Percentage of intercourse attempts lasting > 5 minutes over the treatment assessment period.
15. Proportion of patients improving on PGIS
16. Proportion of patients achieving ≥ 1 category of improvement from baseline to end of treatment in each of the following (from 4-weekly PEP questionnaire):

- a. Satisfaction with sexual intercourse
 - b. Control over ejaculation during sexual intercourse
 - c. Ejaculation-related distress
 - d. Ejaculation-related interpersonal difficulty
 - e. Ejaculation-related bother
17. Change in score from baseline in each of the following (from 4-weekly PEP questionnaire):
- a. Satisfaction with sexual intercourse
 - b. Control over ejaculation during sexual intercourse
 - c. Ejaculation-related distress
 - d. Ejaculation-related interpersonal difficulty
 - e. Ejaculation-related bother

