7.3 Sample Size Calculations

The target total is for 220 patients to be randomized in the study.

The randomization ratio will be 2:2:3:3 (placebo, IX-01 400 mg, IX-01 800 mg, and IX-01 1200 mg dose groups, respectively).

Thus, 44 patients each will be randomized to placebo and IX-01 400 mg dose groups, and 66 patients each will be randomized to IX-01 800 mg and IX-01 1200 mg dose groups. The 2:3 ratio results in only slight loss of statistical power from 1:1 randomization, while increasing the chances that a patient will be randomized to an effective dose of study drug.

Assuming an alpha (2-sided) of 0.05 and an SD of 70 seconds, a sample size of 220 patients randomized in total (44 to the placebo and IX-01 400 mg dose groups and 66 to the IX-01 800 mg and IX-01 1200 mg dose groups) provides approximately 85%, 90%, and 90% power to detect a mean difference of 45 seconds between change from baseline in GM of IELT for the IX-01 400 mg, IX-01 800 mg, and IX-01 1200 mg dose groups, respectively, compared with the placebo group.

Sequential multiplicity control testing of IX-01 1200 mg dose versus placebo, followed by IX-01 800 mg dose versus placebo and then IX-01 400 mg dose versus placebo will be done in order to control for multiplicity. See details below.

Additional patients may be recruited if some patients discontinue from the study with less than 2 postbaseline IELT assessments.

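### The logistic analysis of responder endpoints has no provision for a placebo arm without responders, which at the earlier trial's rate is a 21% to 26% chance for control of ejaculation

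*Combined protocol and SAP*

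**What the plan says.** Protocol section 7.6.2.2 gives one method for all proportion endpoints: the "difference in the proportions between each test group and placebo group will be tested using a logistic model". The model contains treatment, baseline IELT and type of site (site in the synopsis), and the output is P values and adjusted odds ratios. Section 7.6 adds an adjusted effect size with a 95% CI for every treatment comparison. Neither section names the fitting method, the test statistic, or a fallback for an arm with no responders. Section 7.6.2.2 does not pass the matter to the SAP, whereas 7.6.2.1 and 7.6.2.4 do pass details to it.

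On multiplicity, section 7.6.2 says: "The same approach to control for multiple comparisons as proposed for the primary endpoint will be used for each secondary endpoint analysis". Within each endpoint, 1200 mg is therefore tested first, then 800 mg, then 400 mg, all against the same placebo arm.

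Key secondary endpoint 4 (section 7.2.1) is explained as moving from poor or very poor control to fair or better, although its wording also mentions changes of at least 1 or at least 2 categories. For the fair-or-better outcome, section 1.3.5 reports 17 (33%) on IX-01 in the proof-of-concept study, "compared with one (3%) patient randomized to placebo".

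**The concern.** Placebo is one of the two smallest arms and is the comparator for every dose. If an endpoint is nearly empty on placebo, a trial with no placebo responder at all is a realistic outcome. An ordinary logistic fit then cannot deliver the adjusted odds ratios that the plan promises, for any dose. What happens to the P value depends on a choice the section leaves open: a Wald test returns a value near 1, while a likelihood-ratio test from the same model returns a very small one. A key secondary conclusion could turn on a software option, or on a rescue method picked after the empty cell has been seen.

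**Working it through.** **The plan's own power figure.** Section 7.3 says: "Assuming an alpha (2-sided) of 0.05 and an SD of 70 seconds", the sample "provides approximately 85%, 90%, and 90% power to detect a mean difference of 45 seconds". By the normal approximation, power = Φ(45/SE − 1.96):
- 44 vs 44: SE = 70·√(1/44 + 1/44) = 14.92; 45/14.92 = 3.015; Φ(1.055) = 85.4%.
- 44 vs 66: SE = 70·√(1/44 + 1/66) = 13.62; 45/13.62 = 3.303; Φ(1.343) = 91.0%.

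The stated figures are reproduced. They concern the primary endpoint only; section 7.3 gives no power for proportion endpoints.

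**Inputs for the responder endpoint.**
- Placebo n: "44 patients each will be randomized to placebo and IX-01 400 mg dose groups" (section 7.3); 66 each on 800 mg and 1200 mg.
- Placebo rate: 1 patient, printed as 3%. The earlier placebo arm had 23/0.767 = 30 patients (section 1.3.5), so the printed 3% implies a denominator of 29 or 30.
- Active rate: 33% (section 1.3.5).

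**Chance of no placebo responder**, (1 − p)^44:

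| Placebo rate p | Chance of 0 of 44 |
|---|---|
| 3% | 0.97^44 = 26.2% |
| 1/30 | (29/30)^44 = 22.5% |
| 1/29 | (28/29)^44 = 21.4% |
| 13% (CGIC, section 1.3.5) | 0.87^44 = 0.2% |
| 16% (distress, section 1.3.5) | 0.84^44 = 0.05% |

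With 40 evaluable placebo patients (an assumption), the first three rows become 25% to 30%. The exact 95% CI for 1/30 is 0.1% to 17%, which takes the chance from 96% down to almost 0. Averaging over that uncertainty with a Jeffreys prior gives about 26%.

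**Why the odds ratio fails.** With treatment as a factor, maximum likelihood requires the fitted probabilities in the placebo arm to sum to the observed number of responders. No finite coefficients give a sum of 0. Placebo is the reference for all three contrasts, so no dose with responders has a finite odds ratio.

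**Simulation** (44/44/66/66; treatment plus a standardised baseline covariate; 1,500 runs per scenario; repeated with 30 fixed site effects, 300 runs, Wald and likelihood ratio only). Where placebo had 0 responders:
- The 1200 mg log odds ratio reached about 17 to 19 at the iteration limit, with a standard error of about 1,350 to 2,140. The Wald P value was about 0.99 in every such run, with or without site effects.
- The likelihood-ratio P value had a median of about 5 × 10⁻⁷ without site effects.
- Firth's fit gave a finite odds ratio (median about 44), and its penalised likelihood-ratio test was significant in every such run.

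For comparison, 22/66 against 0/44 has a Fisher exact P value of 3 × 10⁻⁶.

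**Power, 1200 mg vs placebo**, model without site effects:

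| Rates, placebo; 400/800/1200 mg | Wald | Likelihood ratio | Firth |
|---|---|---|---|
| 3.3%; 16.7/33/33% | 77% | 99.6% | 99.9% |
| 3.3%; 33/33/33% | 77% | 99.4% | 99.8% |
| 3%; 15/25/33% | 73% | 99.5% | 99.7% |

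The Wald loss is almost entirely the empty cell. In the first row, 21.9% of runs had no placebo responder and Wald power was 99.2% in the rest: (1 − 0.219) × 0.992 = 77.5%. At CGIC rates (13% vs 44%) Wald and Firth agree, at about 95% each.

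**Type I error** with 3.3% or 5% in all arms, nominal 5%, over separate simulation sets of 800 to 2,000 runs: Wald below 1%, likelihood ratio about 6% to 7%, Firth about 2% to 4%.

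**Key secondary endpoint 6.** No earlier rate is given. Exclusion criterion 3 (section 4.1.2) limits entry to poor or very poor control, so a gain of 2 categories always ends at fair or better. Read as a composite, its placebo rate cannot exceed that of endpoint 4 on the fair-or-better reading. At an assumed 1.5%, the chance of an empty cell is 0.985^44 = 51%.

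**The case against.** **The section does not prescribe the test that fails.** A reader might infer that the plan would report a clear difference as non-significant. The text does not support that: it says only a logistic model, and a likelihood-ratio test, an exact method or Firth's method would also fit it. This stands, so the P value problem is conditional on Wald output. The missing finite odds ratio is not, since it follows from any ordinary maximum-likelihood fit.

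**The SAP may deal with it.** The text reviewed holds the protocol only; the separate SAP that it cites was not available. This stands as a limit.

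**The rate is one patient on one reading of one endpoint.** This also stands. If a step from very poor to poor counts under endpoint 4, the 3% does not apply.

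**The damage is contained and visible.** The sequence runs separately for each endpoint, so the primary analysis and other endpoints are untouched. Section 7.6.1 still reports nominal P values and CIs after a stop, and a standard error above 1,000 would be noticed. All true, but noticing it after unblinding leaves only a post hoc rescue.

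**Two stronger readings are not supported.** One is that a more effective drug makes the test fail more often. The driver is a low placebo rate: with placebo at 3.3%, Wald power rises from about 70% to 78% as the dose rate goes from 25% to 33%. The other is to put figures on the long-latency endpoints, such as "Proportion of patients with GM IELT of ≥ 5 minutes over the treatment assessment period". Section 1.3.5 gives mean changes and fold changes without a between-patient spread, and does not say whether they are arithmetic or geometric. Any empty-cell figure at 3, 4 or 5 minutes would rest on those choices. At 4 and 5 minutes, so few active patients may respond that changing the method would recover little.

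**Conclusion.** The concern holds in limited form. Section 7.6.2.2 promises odds ratios that an ordinary fit cannot supply when placebo has no responders. For endpoint 4 on the fair-or-better reading, that has a 21% to 26% chance if the earlier placebo rate carries over and 44 placebo patients are analysed. With Wald tests, power for 1200 mg would be about 73% to 77% instead of 99% or more, and 800 mg and 400 mg could not then be declared significant on that endpoint. An ordinary likelihood-ratio test repairs the P value but not the odds ratio, and is mildly anticonservative in sparse data. Endpoint 6 is probably exposed too, to an unknown degree. At the earlier CGIC and distress placebo rates the issue is negligible. It should be settled before unblinding; it does not threaten the primary analysis.

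**What to change.** In section 7.6.2.2, the synopsis and the SAP, state before unblinding that the proportion endpoints will be fitted by Firth-type penalised logistic regression, with penalised profile-likelihood P values and 95% CIs, and that these P values drive the fixed sequence. Also report the adjusted risk difference with a 95% CI, naming the interval method. It can be estimated with an empty cell and matches the difference in proportions that the section says it tests. A switch to ordinary likelihood-ratio tests alone is not enough, for the reasons above.

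A fallback used only for sparse cells would also work, but one method throughout avoids a data-dependent switch and changes essentially nothing where responders are common.

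The cost is a few sentences and a standard software option. Odds ratios shrink slightly toward 1, and the test is somewhat conservative in the sparsest null case. No patients, visits or data items change.
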